18.5 Grouping of Small Countries

In analyses where country is a factor, countries where not all treatment groups are represented in the APTS will be grouped according to the following stepwise procedure:

- Step 1 All countries where not all treatment groups are represented in the APTS will be grouped into a single collective country within the same continent.
- Step 2 If not all treatment groups are represented in the APTS for a grouped country, the countries will be grouped with the smallest country within the same continent for which all treatment groups are represented in the APTS. If there is more than one such country, the first country in ascending alphabetic order will be selected for the grouping.

Version: 10

LU Study Number: 14861B Trial Site Number: Study Level Pluto ID: CLI 00933680

Status: Final

References

1. United States Food and Drug Administration (FDA). Guidance for Industry: Drug-induced liver injury: Premarketing Clinical Evaluation. July 2009.

LU Study Number: 14861B Trial Site Number: Study Level Pluto ID: CLI 00933680

Appendix II Study Flow Chart

LU Study Number: 14861B Trial Site Number: Study Level Pluto ID: CLI_00933680

Study Flow Chart

Study Procedures and Assessments [open-label treatment period]

Visit	Baseline II ^a	,	Treatme	nt Perio	d	Completion/ Withdrawal ^b	Safety Follow-up ^c	
Visit Number	1	2	3	4	5	6	7	
Day ^d /	0	28/	56/	84/	140/	196/	224/	
End of Week		4	8	12	20	28	32	
Visit Window ^e (days relative to nominal visit)		± 7d	± 7d	± 7d	± 7d	± 7d	+ 7d	
Screening/Baseline Proced	ures and As	ssessmer	nts					
Signed informed consent	√							
Demographics	\sqrt{f}							
Height	\sqrt{f}							
Medical history	\sqrt{f}							
Inclusion/exclusion criteria	$\sqrt{}$							
Efficacy Assessments			*	*				
MMSE	√g					-		
ADAS-Cog	√g			$\sqrt{}$		√		
ADCS-ADL ₂₃	√g					$\sqrt{}$		
ADCS-CGIC ^h	√g			\checkmark		$\sqrt{}$		
NPI	\sqrt{g}			$\sqrt{}$		$\sqrt{}$		
Other Assessments								
RUD Lite	√g			√		√		
EQ-5D-3L	\sqrt{g}			\checkmark		$\sqrt{}$		
Dependence scale	\sqrt{i}			\checkmark		$\sqrt{}$		
Safety Assessments								
Adverse events	\sqrt{j}		√	√	√	√	\sqrt{k}	
Blood and urine sampling								
for clinical safety	lσ	1	1	1	1	1		
laboratory tests	√g . /g	V	V	V	N I	V		
Vital signs, weight, ECGs C-SSRS	√g √g	V	\ !	V	N l	V		
Examinations (physical,	.γ°	٧	٧	٧	٧	V		
neurological)	√g		√		√	√		
Other Study Procedures								
IMP and donepezil ¹	-1	. 1	.1	.1	ا ۽			
hydrochloride dispensed	V	V	√ !	V	N	1		
IMP and donepezil ^l		٧	V	V	V	V		

Page 39 of 48

LU Study Number: 14861B Pluto ID: CLI_00933680

Status: Final

Version: 1.0

Visit	Baseline II ^a	r	Гreatme	nt Perio	d	Completion/ Withdrawal ^b	Safety Follow-up
Visit Number	1	2	3	4	5	6	7
Day ^d /	0	28/	56/	84/	140/	196/	224/
End of Week		4	8	12	20	28	32
Visit Window ^e (days relative to nominal visit)		± 7d	+ 7d				
Screening/Baseline Proced	lures and As	ssessmer	its				
hydrochloride returned accountability tracked							
Recent and concomitant medication	√j	$\sqrt{}$	$\sqrt{}$	$\sqrt{}$	$\sqrt{}$	$\sqrt{}$	\checkmark
Dispense Patient Identification card	$\sqrt{}$						
Patient Identification card returned						\sqrt{m}	
Informed Consent Provided [open-label treatment period with memantine							
period with memantine					ln		

- a. For the purposes of clarity, the Baseline Visit is called Baseline II Visit and this visit is the same as Visit 7 (Completion Visit) in the lead-in study.
- b. This visit should take place as soon as possible after the patient withdraws from the study.
- c. Patients who complete the study and do not enter into the open-label treatment period with memantine (sub-study) will have a Safety Follow-up Visit which is at least 4 weeks (+ up to 7 days) after the last dose of IMP. Patients withdrawn will likewise be followed-up 4 weeks (+ up to 7 days) after withdrawal except for those who withdraw their consent. Patients who withdraw their consent should still have a safety follow-up, but the visit must only be recorded in the medical records.
- d. All assessments can be completed over a maximum of two consecutive days, in this case the first day should be considered as the visit day of the study. Note: If a visit takes place over two consecutive days the IMP should be dispensed on the second day, after all assessments have been performed. For visits other than the Baseline II visit, the visit window must allow for the previously dispensed IMP to last for both visit days.
- e. If the date of a patient visit does not conform to the study plan, subsequent visits should be planned to maintain the visit schedule relative to Baseline II. Number of days between 2 visits must not exceed the number of days for which IMP is provided in the wallet cards.
- f. Lead-in study screening visit (Visit 1) data transferred.
- g. Assessments and procedures conducted at Visit 7 (Completion Visit) of the lead-in study will be transferred and will not be repeated at the Baseline II Visit of this extension study.
- h. During evaluation the patient should be compared to Baseline I assessment of the lead-in study.
- i. Data will be transferred from Visit 7 (Completion Visit) of the lead-in study or entered manually to the eCRF if the scale has been administered for the first time at Visit 1 of the extension study.
- j. On-going adverse events and Concomitant Medications at Visit 7 (Completion Visit) from the lead-in study are to be transferred to the eCRF.
- k. Only for adverse events on-going at Completion/Withdrawal Visit and new SAEs.
- 1. As base treatment, donepezil hydrochloride 10 mg/day will be dispensed as wallet cards.
- m. *Patient Identification Card* should only be returned after the last dose of IMP has been taken, that is at the end of the treatment period.

(substudy)]

n. For patients who may be eligible to participate in the open-label treatment period with memantine (substudy), it is suggested that the *Informed Consent Form* is provided.

LU Study Number: 14861B Pluto ID: CLI_00933680

Status: Final

Page 41 of 48

Study Procedures and Assessments [open-label treatment with memantine (sub-study)]

Visit	Baseline III ^a Treatment Period				Completion/ Safety Withdrawal ^b Follow-up ^c		
Visit Number	6	8 ^j	9	10	11	12	
Day/ ^d	0	224/	252/	280/	364/	392/	
End of Week		32	36	40	52	56	
Visit Window ^e (days relative to nominal visit)		± 7d	±7d	± 7d	±7d	+ 7d	
Screening/Baseline Procedures and Assessments							
Signed informed consent							
Demographics, height	$\sqrt{}$						
Medical history	$\sqrt{}$						
Inclusion/exclusion criteria	$\sqrt{}$						
Efficacy Assessments							
MMSE	√ f				√		
Pharmacoeconomic Assessments							
Patient's current living accommodation (question extracted from the RUD-Lite)	√ f			$\sqrt{}$	V		
Dependence scale	\sqrt{f}			$\sqrt{}$	\checkmark		
Pharmacokinetic Assessments							
Blood sampling for idalopirdine and memantine	√	√	√		√		
Safety Assessments							
Adverse events	\sqrt{f}	√	√		√	$\sqrt{\mathrm{g}}$	
Blood and urine sampling for clinical safety laboratory tests	$\sqrt{\mathrm{f}}$	$\sqrt{}$	$\sqrt{}$	\checkmark	$\sqrt{}$		
Vital signs, weight, ECGs	\sqrt{f}	$\sqrt{}$	\checkmark	$\sqrt{}$	$\sqrt{}$		
C-SSRS	\sqrt{f}	$\sqrt{}$	\checkmark	$\sqrt{}$	$\sqrt{}$		
Examinations (physical, neurological) Other Study Procedures	√ ^f			√ √	√		
IMP and donepezil hydrochloride dispensed. Memantine prescribed h	√	√	√				
IMP, memantine and donepezil hydrochloride returned and accountability tracked h		\checkmark	$\sqrt{}$	$\sqrt{}$	$\sqrt{}$		
Recent and concomitant medication	$\sqrt{\mathrm{f}}$	$\sqrt{}$	\checkmark	$\sqrt{}$	\checkmark		
Dispense Patient Identification card	$\sqrt{}$						
Patient Identification card returned				\sqrt{i}			

LU Study Number: 14861B Pluto ID: CLI_00933680 Status: Final

Trial Site Number: Study Level

Version: 1.0

- a. The Baseline Visit for this study (Baseline III) is the same visit as Visit 6 (end of Week 28) for patients who complete the open-label treatment period.
- b. This visit should take place as soon as possible after the patient withdraws from the study.
- c. Patients who complete the study will have a Safety Follow-up Visit which is at least 4 weeks (+ up to 7 days) after the last dose of IMP. Patients withdrawn will likewise be followed-up 4 weeks (+ up to 7 days) after withdrawal except for those who withdraw their consent. Patients who withdraw their consent should still have a safety follow-up, but the visit must only be recorded in the medical records.
- d. All assessments can be completed over a maximum of two consecutive days, in this case the first day should be considered as the visit day of the study. Note: If a visit takes place over two consecutive days the IMP should be dispensed on the second day, after all assessments have been performed. For visits other than the Baseline Visit of this study, the visit window must allow for the previously dispensed IMP to last for both visit days.
- e. If the date of a patient visit does not conform to the study plan, subsequent visits should be planned to maintain the visit schedule relative to Baseline III of this study. Number of days between 2 visits must not exceed the number of days for which IMP is provided in the wallet cards.
- f. Assessments and procedures are the same as Visit 6 in the open-label treatment period.
- g. Only for adverse events on-going at Completion/Withdrawal of this study and new SAEs.
- h. Donepezil hydrochloride 10 mg/day will be dispensed as wallet cards. Memantine (titration doses plus patient's individualised maintenance dose) will be prescribed by the investigator or another medically-qualified person and the investigator should make sure that an adequate supply of memantine is prescribed to last between two visits (including visit windows). In addition to the return of IMP and donepezil hydrochloride, patient will be asked to bring used and unused memantine in original packaging to the visit for accountability purposes.
- i. *Patient Identification Card* should only be returned after the last dose of IMP has been taken, that is at the end of the treatment period.
- j. All patients entering the open-label treatment period with memantine (sub-study) will perform Visit 8 right after Visit 6 [Visit 7 is the Safety Follow-up visit only for patients who do not continue into the open-label treatment period with memantine (sub-study)].

LU Study Number: 14861B Trial Site Number: Study Level Pluto ID: CLI 00933680

Appendix III SAS® Code

LU Study Number: 14861B Pluto ID: CLI_00933680

Status: Final Version: 1.0

SAS® Code

```
The SAS code for the MMRM-analysis (for each lead-in study) will be:

%**MMSTR=MMSE stratum;

proc mixed noclprint data=ADAS ic method=REML;

class usubjid country analysis_week armcd MMSSTR;

model ADASTOT_DL = ADASTOT_BL MMSSTR country armcd analysis_week

armcd*analysis_week MMSSTR*analysis_week ADASTOT_BL*analysis_week

/s DDFM=KR;

repeated analysis_week/subject=usubjid type=un;

run;
```

Page 45 of 48 LU Study Number: 14861B Trial Site Number: Study Level

Status: Final Version: 1.0

Pluto ID: CLI 00933680

Appendix IV PCS Criteria

LU Study Number: 14861B Trial Site Number: Study Level Pluto ID: CLI_00933680

PCS Criteria

Table 1 PCS Criteria for Clinical Safety Laboratory Tests

CDISC term	Test (units)	PCS Low	PCS High
Liver			
AST	S-aspartate aminotransferase (IU/L)		$\geq 3 \times ULN$
ALT	S-alanine aminotransferase (IU/L)		\geq 3 × ULN
BILI	S-bilirubin (μmol/L)		≥ 34
BILDIR	S-direct bilirubin (µmol/L)		≥ 12
ALP	S-alkaline phosphatase (IU/L)		$\geq 3 \times ULN$
GGT	S-gamma glutamyl transferase (IU/L)		≥ 200
Kidney			
CREAT	S-creatinine (µmol/L)		$\geq 1.5 \times ULN$
BUN	B-urea nitrogen (mmol/L)		≥ 11
Electrolytes			
SODIUM	S-sodium (mmol/L)	≤ 125	≥ 155
K	S-potassium (mmol/L)	≤ 3.0	≥ 6.0
CA	S-calcium (mmol/L)	≤ 1.8	≥ 3.0
BICARB	S-bicarbonate (mmol/L)	≤ 12	≥ 38
Endocrine/Meta	bolic		
GLUC	Serum glucose (mmol/L)	≤ 3.9	≥ 11.1
GLUC	Serum glucose, fasting (mmol/L)	≤ 3.5	≥ 7.0
TSH	S-thyrotropin (mIU/L)	≤ 0.3	≥ 5.5
ALB	Albumin (g/L)	≤ 27	
Lipids			
CHOL	S-cholesterol (mmol/L)		≥ 7.8
CHOL	S-Cholesterol, fasting (mmol/L)		≥ 6.2
TRIG	Triglycerides (mmol/L)		≥ 5.65
TRIG	Triglycerides, fasting (mmol/L)		≥ 4.2
Haematology/Co	pagulation		
INR	P-INR (Prothrombin ratio)		≥ 2.0
PLAT	B-thrombocytes platelet count (×10E9/L)	≤ 75	≥ 600
HGB	B-haemoglobin (g/dL)	≤ 9.5 (women) ≤ 11.5 (men)	≥ 16.5 (women) ≥ 18.5 (men)
RBC	B-erythrocytes (×10E12/L)	≤ 3.5 (women) ≤ 3.8 (men)	\geq 6.0 (women) \geq 7.0 (men)
WBC	B-Leukocytes (×10E9/L)	\leq 2.8	≥ 16
NEUTLE	B-Neutrophils/leukocytes (%)	≤ 20	≥ 85
EOSLE	B-eosinophils/leukocytes (%)		≥ 10

Page 47 of 48

LU Study Number: 14861B Pluto ID: CLI_00933680

Status: Final

Version: 1.0

CDISC term	Test (units)	PCS Low	PCS High
BASOLE	B-basophils/leukocytes (%)		≥ 10
LYMLE	B-Lymphocytes/leukocytes (%)	≤ 10	≥ 75
MONOLE	B-Monocytes /leukocytes (%)		≥ 15
Infection			
CRP	S-C-reactive protein (mg/L)		≥ 25
Urine			
GLUC	U-Glucose		Increase≥2
KETONES	U-Ketones		Increase≥2
OCCBLD	U-Occult Blood		Increase≥2

Table 2 PCS Criteria for Vital Signs and Weight

CDISC term	Variable (units)	PCS Criterion Low	PCS Criterion High
WEIGHT	Weight (kg)	Decrease ≥ 7%	Increase ≥ 7%
BMI	Body mass index (kg/m2)	Decrease $\geq 7\%$	Increase $\geq 7\%$
DIABP	Supine diastolic blood pressure (mmHg)	\leq 50 and decrease \geq 15	≥ 105 and increase ≥ 15
SYSBP	Supine systolic blood pressure (mmHg)	\leq 90 and decrease \geq 20	≥ 180 and increase ≥ 20
PULSE	Pulse rate supine/sitting/unknown (bpm)	\leq 50 and decrease \geq 15	\geq 120 and increase \geq 15

Table 3 PCS Criteria for ECG Parameters

CDISC term	Parameter (units)	PCS Criterion Low	PCS Criterion High
Absolute Time Int	erval		
PRMEAN	PR interval (msec)		≥ 260
QRSDUR	QRS interval (msec)		≥ 150
QTMEAN	QT interval (msec)		≥ 500
Derived Time Inte	rval		
QTcB	QTcB interval (msec)	< 300	> 500 or increase > 60
QTcF	QTcF interval (msec)	< 300	> 500 or increase > 60
HRMEAN	ECG Mean heart rate (beats/min)	\leq 50 and decrease \geq 15	\geq 120 and increase \geq 15

Trial Site Number: Study Level

Version: 1.0

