1.1.2 Non-clinical Data

Idalopirdine is a high affinity antagonist for the 5-HT₆ receptor. Broad profiling of idalopirdine in more than 100 additional assays demonstrated medium affinity to the adrenergic α -1A and α -1B receptors and to the dopamine D3 receptor. Efficacy profiling showed that idalopirdine was an antagonist for the adrenergic α -1A, α -1B and dopamine D3 receptors. For all the remaining targets tested, idalopirdine demonstrated at least 100-fold selectivity.

Idalopirdine has been shown to improve performance in multiple rodent cognition tasks. In doses leading to >65% striatal 5-HT₆ receptor occupancy *in vivo*, idalopirdine reversed

cognitive impairment induced by subchronic phencyclidine in rats. There is no preclinical evidence to demonstrate the cognitive benefits of concomitant treatment of idalopirdine, donepezil and memantine. In microdialysis studies, administration of idalopirdine alone did not affect extracellular levels of GABA, dopamine, 5-HT or acetylcholine (ACh) in the rat prefrontal cortex, whereas idalopirdine (5 mg/kg per os) significantly potentiated donepezil-induced increases in extracellular levels of ACh. This suggests the possibility of synergistic effects when combining idalopirdine with acetylcholine esterase inhibitors.

Safety pharmacology and toxicology studies indicate that at clinically relevant exposure levels, idalopirdine is well tolerated. Multiple-dose toxicology studies were conducted in rats and monkeys at doses up to 250 mg/kg and 50 mg/kg, respectively. In monkeys, convulsions occurred at high exposure levels. In rats, increased blood clotting time was noticed at high exposure levels.

Exploratory data using human recombinant enzymes indicated that cytochrome P450 isoenzyme (CYP) 3A4 was the major CYP450 enzyme involved in the metabolism of idalopirdine with some contribution from CYP1A2, CYP2C9, CYP2C19, and CYP2D6. Idalopirdine showed inhibitory potential towards CYP2D6. Furthermore, in an *in vitro* study evaluating the induction potential of idalopirdine, idalopirdine showed little (CYP2B6 and CYP2C8) or no induction potential (CYP1A2, CYP2B6, CYP2C8, CYP2C9, CYP2C19, CYP2D6 and CYP3A4/5) towards the CYPs investigated.

Further information can be found in the *IB*.¹

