5.4 Withdrawal Criteria

A patient must be withdrawn from the study if:

- the patient and/or his or her legal representative withdraws his or her consent (defined as a patient and/or his or her legal representative who explicitly takes back his or her consent); section 8.3 states how the patient's data will be handled.
- the investigator considers it, for safety and/or study compliance reasons, in the best interests of the patient that he or she be withdrawn.
- the patient has a serum ALT or AST value >8 times the upper limit of the reference range.* (Not applicable for the Czech Republic)
- the patient has a serum ALT or AST value >5 times the upper limit of the reference range that is confirmed by testing within 5 days. (Applicable for the Czech Republic only)
- the patient has a serum ALT or AST value >3 times the upper limit of the reference range and a serum total bilirubin value >2 times the upper limit of the reference range.*
- the patient has a serum ALT or AST value >3 times the upper limit of the reference range and an international normalised ratio of prothrombin time (INR) more than 1.5.*
- the patient has a serum ALT or AST value >5 times the upper limit of the reference range for >2 weeks.* (Not applicable for the Czech Republic)
- the patient has a serum ALT or AST value >3 times the upper limit of the reference range with the appearance of fatigue, nauseas, vomiting, right upper quadrant pain or tenderness, fever, rash, and/or eosinophilia (>5%).*
- the patient has a QTcF interval >500 ms that is confirmed with an ECG taken at a visit <2 weeks later.
- the patient attempts suicide or is at significant risk of suicide (either in the opinion of the investigator or defined as a "yes" to suicidal ideation questions 4 or 5 or answering "yes" to suicidal behaviour on the C-SSRS during the study).

- the patient is lost to follow-up (defined as a patient who fails to comply with scheduled study visits or contact, who has not actively withdrawn from the study, and for whom no alternative contact information is available [this implies that at least two attempts have been made to contact the patient]).
 - * in accordance with the FDA "Guidance for Industry Drug-Induced Liver Injury: Premarketing Clinical Evaluation"⁵

Patients who withdraw will not be replaced.

6 Investigational Medicinal Products

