16.9.2 Analysis of Other Safety Endpoints

Clinical safety laboratory tests, vital signs, weight and ECG parameters will be summarised by visit and last post baseline assessment in the treatment period. For the open-label treatment period (initial 28-week period), the summaries will be presented using data from both the lead-in study and the open-label treatment period (initial 28-week period).

Potentially clinically significant (PCS) values will be flagged and summarised.

If relevant, individual patient profile plots will be generated for selected parameters, using data from both the lead-in study and the extension study.

C-SSRS will be summarised by visit. For the open-label treatment period (initial 28-week period), the summaries will be presented using data from both the lead-in study and the open-label treatment period (initial 28-week period).

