Appendix II

Recent and Concomitant Medication: Disallowed or Allowed with Restrictions

Recent and Concomitant Medication: Disallowed or Allowed with Restrictions

In the table below disallowed recent and concomitant medications are listed, including any restrictions with respect to their use prior to and during the study.

Disanowed Recent and Concomitant Medication		
Drug Class	Details	
Any investigational drug	Disallowed throughout the whole study.	
AChE inhibitors or cholinergic	All AChE inhibitors except donepezil are disallowed. Treatment with	
agonists or antagonists	donepezil must have been stable at 10 mg/day and must be maintained	
	throughout the duration of the study.	
Anti-cholinergic drugs acting on	Allowed only if prescribed for urinary and bladder difficulties, including	
the muscarinic acetylcholine	frequent urination and inability to control urination. Dose modifications and	
receptor	initiation of treatment are disallowed during the study.	
Anaesthetics:		
General	General anaesthetics are disallowed during the study except in case of	
Local	emergency procedures requiring anaesthesia.	
	Episodic use of local anaesthetics is allowed.	
Analgesics	Codeine and tramadol are allowed. Other opioid analgesics are disallowed	
	during the study.	
Anorexics	Disallowed during the study.	
Antiacne agents	Disallowed during the study.	
	Agents for topical use are allowed.	
Antiarrhythmics	Open-label treatment period (initial 28-week period):	
	Flecainide and propafenone disallowed. For other antiarrhythmics dose	
	modifications and initiation of treatment are allowed during the study. As	
	specified in the donepezil SPC precaution should be taken when administering	
	quinidine.	
	Open-label treatment period with memantine (substudy):	
	Flecainide, quinidine and propafenone disallowed. For other antiarrhythmics	
	dose modifications and initiation of treatment are allowed during the study.	
	Procainamide is allowed but caution should be exercised according to the	
	memantine SmPC.	
Antibiotics	Disallowed for chronic use during the study.	
	UTI prophylaxis with antibiotics is allowed.	
Anticoagulants	Low dose Low Molecular Weight Heparins for deep vein thrombosis	
-	prophylaxis are allowed. The anti-aggregation agents clopidogrel, or aspirin,	
	or dipyridamole are allowed. Other anticoagulants are disallowed during the	
	study.	
Anticonvulsants	Disallowed if indication is epilepsy or convulsions.	

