11.1.11 Adverse Events of Special Interest

The following standardized MedDRA queries (SMQ) will be summarised in total and by preferred term:

- Convulsions (narrow scope)
- Drug-related hepatic disorders -comprehensive search
- Haemorrhages (broad scope)

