11.2 General Methodology for Other Safety Data

The denominators for the summaries of a given variable will be based on the number of patients with non-missing values at a given visit or during the assessment period.

Descriptive statistics for the safety variables in the open label treatment period, absolute values changes from both Baseline I and Baseline II, will be presented by visit and the last post-baseline assessment in the treatment period.

For the open-label treatment period with memantine, summaries will be presented for absolute values and change from Baseline III by visit and last assessment in the treatment period.

The number and percentage of patients with at least one PCS value at any post-Baseline II assessment in the open-label treatment period will be summarised by variable. The number and percentage of patients with at least one PCS value at any post-Baseline III assessment in the open-label treatment period with memantine will be summarised by variable . All available assessments will be included in the evaluation of PCS values (scheduled, reassessments, and unscheduled). For tests where PCS is defined as a change, the summaries will be prepared both for PCS compared to baseline I and baseline II for the open label treatment period.

For patients with post-baseline II PCS values (compared to baseline II) in the open-label treatment period, listings will be provided including all available values for the variable, with

LU Study Number: 14861B Trial Site Number: Study Level Pluto ID: CLI 00933680

Page 18 of 48

flagging of PCS values and out-of-reference-range values. The corresponding listings will be prepared for the open label treatment period with memantine.

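### aPTT is the only protocol blood test without a PCS criterion in the SAP, so prolonged values are not counted or listed from the laboratory data

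*SAP*

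**What the plan says.** **Protocol.** Section 1.1.2 reports: "In rats, increased blood clotting time was noticed at high exposure levels". Panel 5 (section 9.4.2) lists P-INR and aPTT under coagulation, and Panel 2 schedules safety laboratory sampling at Visits 1 to 6. Section 16.9.2 commits that "Potentially clinically significant (PCS) values will be flagged and summarised". Section 16.9.3 lists joint liver criteria. One combines ALT or AST above 3 × ULN, either bilirubin above 2 × ULN or INR above 1.5 × ULN, and AP no higher than 1.5 × ULN. Section 5.4 pairs ALT or AST above 3 × ULN with "an international normalised ratio of prothrombin time (INR) more than 1.5". On anticoagulants, after naming the permitted agents, Appendix II says "Other anticoagulants are disallowed during the" study.

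**SAP.** Section 11.2 summarises the "number and percentage of patients with at least one PCS value at any post-Baseline II assessment in the open-label treatment period". For patients with such a value, "listings will be provided including all available values for the variable", with PCS and out-of-range results flagged. It also lists these patients' adverse events, with the PCS value placed next to events in the same visit window. The substudy is handled in the same way from Baseline III. The limits are in Appendix IV, Table 1, where the only clotting-time row begins "P-INR (Prothrombin ratio" and has a PCS High limit of 2.0 or more. Section 11.1.11 includes a bleeding query among the events of special interest, beginning "Haemorrhages (broad scope". Section 17 declares one departure from the protocol's analyses, which concerns the C-SSRS.

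**The concern.** PCS limits pick out individual patients with abnormal results by a rule fixed in advance, whatever the investigator thinks of each value. A test without a limit falls outside that screen. Here the test is one of only two that measure clotting, in a study whose primary objective is safety and whose SAP singles out bleeding events. If a few patients developed a prolonged aPTT, no planned laboratory table would say how many, no laboratory listing would identify them, and no output would set their values beside any bleed. A report could then describe coagulation as unremarkable although individual patients had not been screened on aPTT.

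**Working it through.** **1. Panel 5 against Table 1.**

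| Panel 5 group | Blood tests | With a PCS limit in Table 1 |
|---|---|---|
| Haematology | 8 | 8 |
| Lipids | 2 | 2 |
| Infection (CRP) | 1 | 1 |
| Liver | 6 | 6 |
| Electrolytes | 4 | 4 |
| Metabolic | 2 | 2 |
| Kidney | 2 | 2 |
| Coagulation | 2 | 1 (INR only) |
| Total | 27 | 26 |

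The one blood test left over is aPTT. Urine protein also has no row, but SAP 11.3.2 gives dipstick tests their own categorical summaries by visit. aPTT has no such substitute. Table 1 reads continuously across its page break, so nothing suggests that a row was lost.

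**2. Routes by which an aPTT value can reach an output.**

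- PCS count, PCS listing and adverse events beside PCS values (SAP 11.2): closed, because each needs a PCS limit. Out-of-range flags appear only inside the PCS listing.
- Separate tables with the worst value (SAP 11.3.1): closed. They cover GGT, ALT, AST, ALP, bilirubin and eosinophils.
- Individual plots: protocol 16.9.2 allows them for selected parameters if relevant. The SAP specifies them for liver tests (with eosinophils), weight, heart rate and QTcF, not for coagulation.
- Descriptive summaries (SAP 5 and 11.2): open. They give quartiles, minimum and maximum by visit and at the last assessment. Under SAP 18.3.2 a post-baseline visit uses the first usable scheduled result, whereas the PCS evaluation also takes in reassessments and unscheduled samples. A prolonged value found only on an extra sample may therefore not enter the by-visit figures.
- Adverse event reporting (protocol 9.4.2; SAP 11.1.5 and 11.1.6): open, but only for values that the investigator judges clinically significant.

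**3. Number of values without the screen.** The plan's own base is 3 × 310 + 3 × 280 = 1,770 lead-in patients. Its completer figure reproduces: 1,770 × 0.85 × 0.85 = 1,278.8, about 1,280.

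- Upper figure: 1,770 × 0.85 = 1,504.5, about 1,505 lead-in completers. Visits 2 to 6 are the five scheduled samples after Baseline II; Visit 1 is the transferred lead-in sample. 1,504.5 × 5 = 7,522.5, about 7,500 values.
- Completers of the initial period alone: 1,278.8 × 5 = 6,394, about 6,400 values.
- The substudy adds up to about 100 × 4 (Visits 8 to 11) = 400.

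These are values measured, not values prolonged. The documents give nothing from which to derive the number prolonged.

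**4. The INR liver criterion.** SAP 11.3.3 carries the bilirubin-based joint criteria and adds others on GGT and eosinophils, but none contains INR. Take a patient with ALT or AST above 3 × ULN, INR above 1.5 × ULN, bilirubin at or below 2 × ULN and AP at or below 1.5 × ULN. The protocol's criterion counts this patient; no joint criterion in the SAP does. Section 17 does not mention the change.

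**The case against.** The strongest reply is that such patients are not invisible. Investigators must classify every out-of-range result, and those judged clinically significant become adverse events, which are listed in full and, when treatment-emergent, counted by preferred term. Listings run by patient, so a reported aPTT abnormality and a bleed in the same person would appear together. The summaries also show the maximum at each visit. All of this stands. A reader might infer that prolonged aPTT is never counted or listed, or that only group means would reveal it; the documents support neither. What remains missing is a count that does not rest on investigator judgement in an open-label study. A maximum shows one extreme value, not how many patients or which.

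The signal is also weak. The rat finding arose at high exposure, and the same section calls the drug well tolerated at clinically relevant levels. Protocol 1.1.3.3 reports only small laboratory changes apart from liver tests, without trends, at 90 mg/day in the phase II Alzheimer's study. That limits the weight of the point but does not explain leaving out one test of 27. Nor do the documents say that coagulation tests or the bleeding query were chosen because of the rat finding; that link would be inference.

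Finally, a reader might take 1.5 as the protocol's INR limit and call 2.0 too lax. The documents do not support 1.5 as a stand-alone PCS limit: sections 5.4 and 16.9.3 use it only jointly with ALT or AST above 3 × ULN, as a liver criterion.

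**Conclusion.** The point holds in limited form. aPTT is collected, has no PCS limit, and so drops out of every patient-level output driven by laboratory data; the SAP neither declares nor explains this. In the initial period it affects at most about 7,500 scheduled values. That figure assumes the plan's 85% lead-in completion, entry of every completer, the full Panel 5 at each laboratory visit and no dropout. It is an upper bound on values left unscreened and says nothing about how many would be abnormal. No passage promises a PCS limit for every test, so this is a gap in the safety screen rather than a breach of the protocol. It is worth closing because safety is the primary objective, bleeding is an event of special interest, and most anticoagulants are disallowed, which leaves fewer drug explanations for a prolonged value. The missing INR liver criterion is a separate, undeclared departure from protocol 16.9.3.

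**What to change.** 1. Add an aPTT row to SAP Table 1 with a PCS High limit as a multiple of ULN, set by the sponsor before analysis. Alternatively, add to SAP 11.2 a count and listing of patients with aPTT above the reference range.
2. Under either option, include those patients in the SAP 11.2 listing of adverse events beside PCS values, in both treatment periods, so that any bleeding event appears next to the result.
3. Restore the joint criterion with INR above 1.5 × ULN from protocol 16.9.3 to SAP 11.3.3, or explain its removal in section 17. Leave the stand-alone INR limit as it is.

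The data are already collected. The cost is one or two table rows, one more joint criterion and a few more flagged values to review.
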